2.10.2 Modified Intent-to-Treat (mITT) Population

The mITT population is defined to include all subjects enrolled who received at least one vaccination. Subjects will be analyzed according to the treatment group they had been allocated to, rather than by the actual treatment, they received.

If the Safety and mITT Population are identical (i.e. no mis-randomization) the analysis will be performed for the Safety Population and the mITT Population together, labeled with "Safety/mITT Population".

2.10.3 Per-Protocol (PP) Population

The Per-Protocol (PP) Population will exclude all subjects from the mITT that fulfilled at least one of the major protocol deviation criteria as defined in Section 2.8. The PP Population will be defined in the BDRM that is conducted before IA Day 85. A second DRM is planned prior to the final analysis to review protocol deviations after the interim analysis.

2.11 Subject Data Listings

All vaccinated subjects will be included in the listings if not stated otherwise. Data listings will include the subject number as identifier (and parameter and/or visit if available) and will be sorted by subject ID (and parameter and/or visit if available). A column showing the treatment group will be shown in all listings. Additionally, a column indicating if a subject is in the PP Population will be shown in all immunogenicity listings.

2.12 Columns in Tables

All tables will be presented by treatment group, i.e. every treatment group will be shown in a separate column. Tables described at overall study information (Section 3), baseline evaluation (Section 4) and safety analysis (Section 6) will show one column per treatment group (i.e. 90 µg, 135 µg, 180 µg and Placebo) a column for the three VLA15 treatment groups pooled and a column for all subjects pooled. Tables defined in Section 5 will show one column for each treatment group. Statistical analyses will pool subjects from both Run-in and Main Study phase.

2.13 Medical Coding

Adverse events, medical history and concomitant procedures will be coded using Medical Dictionary for Regulatory Activities (MedDRA) and concomitant medications and vaccination history will be coded using WHO Drug Reference List and Anatomical Therapeutic Chemical (ATC) Classification System as described in the Coding Guideline.

Events reported in the adverse events log will be combined with solicited symptoms from the diary section. Solicited symptoms will be coded as described in Section 6.1.2.2.

2.14 Changes in the Conduct of the Study or Planned Analysis

Statistical analysis will be conducted as described in this SAP. Any deviations or changes will be described and justified in the CSR.

- It was stated in the protocol that an interim analysis on safety and immunogenicity data will be performed after all subjects have completed Visit 6 (i.e. Day 236, six months after the last vaccination) and that this interim analysis will cover safety and immunogenicity data up to Visit 4 as well as safety data up to Visit 6. This interim analysis will be conducted in 2 parts, a IA Day 85 covering all safety data up to Day 85 and immunogenicity data from Day 1 and Day 85. The second part will cover all safety data up to Day 236 (see Section 2.1). The first part of the Interim Analysis only starts after the last subject completed Visit 6 or the time window for Visit 6 has elapsed.

- The following adjustments concerning statistical analysis as compared to descriptions in the protocol are included in this SAP: The protocol planned to only compare the two dose groups selected for the main phase and the placebo group. However, it was decided to include all dose groups in the comparison. In particular, the pair-wise comparison between the two dose groups selected for the main phase and the placebo group, respectively, will be part of the comparisons that will be performed.
- It was stated in the protocol that all time points up to Day 85 will be included in interim immunogenicity analysis. However, only Day 1 and Day 85 will be analyzed in the IA Day 85. All time points will be analyzed in the Final Analysis.
- Due to optimization of the ELISA assay, the definition for seroconversion for ELISA results was adjusted as compared to the protocol, see Section 5.2.
- Functionality of antibodies will be measured by a Serum Bactericidal Assay (SBA). Analysis of SBA parameters will be described in a separate SAP and is not part of the interim analysis described here.

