1.2 Study Design

This is a randomized, observer-blind (subject, sponsor and investigator/ site staff involved in clinical evaluation of subjects are blinded), placebo controlled, multicenter Phase 2 study (see Figure 1).

In the Run-in phase, a total of 120 subjects aged 18 to 40 years were to be randomized stratified by study site 1:1:1:1 to receive VLA15 90 µg w/ alum, VLA15 135 µg w/ alum, VLA15 180 µg w/ alum, or placebo (30 subjects per treatment group) as intramuscular (I.M.) vaccinations on Days 1, 29 and 57. Dosing was to be adjusted by injection volume (see Table 1).

Table 1: Treatment Groups and Vaccinations

Group	Treatment	Injection Volume [mL]	Days of Vaccination
90 µg	VLA15 90 µg w/ alum	0.50	1, 29, 57
135 µg	VLA15 135 µg w/ alum	0.75	1, 29, 57
180 µg	VLA15 180 µg w/ alum	1.00	1, 29, 57
Placebo	PBS	1.00	1, 29, 57

Two safety visits were to be performed after the first vaccination: a safety phone call at Day 4 (i.e. Visit 1a, three days after the first vaccination) and an in-person visit at Day 8 (i.e. Visit 1b, seven days after the first vaccination). After all subjects enrolled in the Run-in phase completed Visit 4 (Day 85, i.e. 28 days after the third vaccination) a Data Safety Monitoring Board (DSMB) reviewed all available safety data up to Day 85 in a scheduled DSMB meeting and gave the recommendation that all treatment groups were safe and well tolerated so far and could be continued in the Main Study phase based on available safety data. After the DSMB meeting, the two higher dose groups (135 µg and 180 µg of VLA15 w/ alum) were selected for further investigation. No safety concerns associated with any of the VLA15 treatment groups were identified by the independent DSMB.

In the Main Study phase, a total of 450 subjects aged 18 to 65 years will be randomized stratified by study site, age group and baseline *B.b. s.l.* serostatus 2:2:1 to receive 135 µg or 180 µg VLA15 w/ alum (180 subjects each) or placebo (90 subjects), as I.M. vaccinations on Days 1, 29 and 57. Subjects will be enrolled in two age groups (18-49 years and 50-65 years) in a ratio of approximately 2:1.

In both study phases, target is to enroll approximately 10 % or more of subjects that are baseline seropositive for *Borrelia burgdorferi sensu latu* (*Bb s.l.*). This is aimed to be achieved through selection of endemic recruitment areas as well as database searches for *Bb s.l.* seropositive subjects.

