5.3 Inferential analysis

- In general, all statistical tests comparing treatment groups in the immunogenicity analysis will only include the two dose groups chosen for the main phase (i.e. VLA15 135 μ g and 180 μ g groups) and the placebo group. However, summary measures for 90 μ g group will be included in the tables.
- ANOVAs with factors treatment group and study sites will be performed for the comparison between the VLA15 135 μ g, 180 μ g and Placebo group for each OspA ST1 to ST6 respectively. The primary immunogenicity analysis will be the ANOVA for ELISA GMTs at Day 85 in the PP Population.
- ANOVAs will be performed for GMTs as well as GMFRs at all available time points.
- This will be done using log10 transformed data and taking the anti-log of the resulting point estimates for the least squares means, least squares means differences and the corresponding 95% CIs. Tukey's HSD test will be applied for pair-wise comparisons.
- Sensitivity analyses for GMTs and GMFRs will be performed for ANOVAs with factors study site, treatment group, study site*treatment group, age, and B.b. s.I serostatus at baseline.
- Summary tables for the OspA- specific IgG titer against each OspA serotype and summary tables for the geometric mean fold-rise against each OspA serotype will be amended by an overall test (Kruskal-Wallis).
- SCRs will be compared using Fisher-Freeman-Halton tests, a significant overall test will be amended by pair-wise tests (Fisher's exact test). The same will be done for rates of subjects reaching a 4- or 10- fold Increase from Day 1 (Visit 1) in titer.
- A non-parametric correlation analysis (Spearman) between OspA IgG antibodies GMTs for each combination of two different OspA specific IgG types will be performed for Day 85 and VLA15 treatment group separately as well as for all VLA15 treatment groups together (pooled analysis).

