6.1.3 Inferential Analysis for Adverse Events

95% confidence intervals according to Altman will generally be provided for all AE rates. Differences between the four treatment groups will be assessed for significance using Fisher's exact (Fisher-Freeman-Halton) test, whereby a significant overall test will be amended by pair-wise tests.

It is stated in detail in Section 7 for which tables such comparisons will be made.

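### Sections 2.14 and 5.3 disagree on whether 90 µg enters the comparisons, and Section 6.1.3 makes every pair-wise AE test depend on a four-group test that includes a Run-in-only 90 µg group

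*SAP*

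**What the plan says.** **Which groups are compared.** SAP Section 2.14 lists adjustments that this SAP makes to the protocol's analysis. It says that the protocol compared only the two main-phase doses and placebo, and continues: "However, it was decided to include all dose groups in the comparison". The dose-placebo pairs are described as one part of the comparisons to be made. Nothing restricts the sentence to safety or to immunogenicity.

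SAP Section 5.3 says: "In general, all statistical tests comparing treatment groups in the immunogenicity analysis will only include the two dose groups chosen for the main phase", together with placebo. For 90 µg it promises summary measures only. Its ANOVA bullet names the same three groups again and identifies the Day 85 GMT ANOVA in the PP Population as primary. For that ANOVA, Tukey's "HSD test will be applied for pair-wise comparisons".

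**AE tests.** SAP Section 6.1.3 says: "Differences between the four treatment groups will be assessed for significance using" a Fisher-Freeman-Halton test, "whereby a significant overall test will be amended by pair-wise tests". Section 2.12 adds: "Statistical analyses will pool subjects from both Run-in and Main Study phase".

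**Where the groups come from (Section 1.2).** In the Run-in phase, "a total of 120 subjects aged 18 to 40 years were to be randomized stratified by study site 1:1:1:1", which gives 30 each on 90, 135 and 180 µg and placebo. "In the Main Study phase, a total of 450 subjects aged 18 to 65 years will be randomized" 2:2:1 to 135 µg, 180 µg and placebo, with no 90 µg arm.

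**The concern.** Section 2.14 describes what the current SAP contains, so this is not a difference between live text and superseded text. Section 5.3 keeps the three-group plan that Section 2.14 says was replaced. The number of groups sets the Tukey critical value, so the primary analysis gives different adjusted intervals and p-values depending on which section is programmed.

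In safety the text is clear but the construction is weak. 90 µg was randomised only in the Run-in phase, among subjects aged 18-40, while most of its pooled comparators were enrolled later and are aged up to 65. A 90 µg p-value can therefore reflect period or age as well as dose. Because the four-group test is a gate, the 90 µg result also helps decide whether 135 µg, 180 µg and placebo are compared with each other at all.

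**Working it through.** **1. The plan's own figure (Section 1.4).** Inputs: GMTs 61.3 and 86.1, SD (log10) 0.51, 189 per group, two-sided 5%.
- Difference: log10(86.1/61.3) = 0.1475.
- n per group = 2 × ((1.960 + 0.842) × 0.51 / 0.1475)² = 188.
- Power at 189 = 80.3%. The stated 80% reproduces, for a single unadjusted two-group comparison.

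**2. Effect of the group count on Tukey.** Noncentrality = 0.1475 / (0.51 × √(2/189)) = 2.812. The critical t is the studentized-range quantile divided by √2. I assume 10% PP exclusion in every group, giving 189, 189 and 108 (placebo), plus 27 (90 µg) where it is included. Site terms are ignored in the degrees of freedom.

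| Groups | df | Critical t | Power, 86.1 vs 61.3 |
|---|---|---|---|
| 3 (Section 5.3) | 483 | 2.351 | 67.8% |
| 4 (Section 2.14) | 509 | 2.578 | 59.3% |

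**3. Composition of the pooled groups.**

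| Group | Run-in | Main Study | Main Study share |
|---|---|---|---|
| 90 µg | 30 | 0 | 0% |
| 135 µg, 180 µg (each) | 30 | 180 | 180/210 = 86% |
| Placebo | 30 | 90 | 90/120 = 75% |

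**4. The gate can switch on the 90 µg result.** Two invented tables with n = 30/210/210/120, exact Fisher-Freeman-Halton test:
- Events 3/21/24/4 (90, 135, 180 µg, placebo): p = 0.056 with four groups, 0.027 with three. The 90 µg group closes the gate.
- Events 10/21/21/8: p = 0.0024 with four groups, 0.56 with three. The 90 µg group opens it.

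**5. How often, under assumed rates.** The SAP gives no AE rates. I assume a 35% Main Study rate, no dose effect, and a Run-in rate higher by the stated gap. Each scenario is 100,000 simulated trials, with exact overall tests at 5% followed by Fisher pairs.

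| Phase gap (points) | 0 | 5 | 10 |
|---|---|---|---|
| Four-group overall test significant | 5.0% | 6.5% | 10.9% |
| Three-group overall test significant | 5.1% | 5.0% | 5.3% |
| False 90 µg signal (gate plus a 90 µg pair) | 2.8% | 4.3% | 8.8% |
| False pair among 135, 180, placebo, four-group gate | 3.7% | 4.1% | 5.2% |
| Same, three-group gate | 5.1% | 5.0% | 5.3% |

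**6. Age alone.** With assumed younger/older rates of 40/25, 60/40 and 60/30%, a false 90 µg signal arises in 4.3, 4.6 and 7.4% of trials in the pooled tables.

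**7. Power cost of the gate with no phase gap.**
- 180 µg at 47%, all other groups 35%: 180 vs 135 µg is declared different in 57.6% (four-group gate) vs 62.0% (three-group gate), a loss of 4.4 points.
- Placebo 25%, all doses 35%: any significant placebo contrast in 37.7% vs 44.0%, a loss of 6.3 points.

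**The case against.** **On the contradiction.** Section 5.3 is specific, names its three groups twice and gives 90 µg summary measures only. A careful programmer would follow it, and Section 2.14 may have been written with the four-group AE tests in mind. That stands: three groups is the likelier intent, and the 59.3% arises only if Section 5.3 is not followed. A reader might infer that the primary analysis has lost that power. The documents do not support this. They support only that two current sentences need to agree.

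**On age.** The SAP already plans tested AE tables by age group: 14.1.4.2, 14.1.4.17, 14.1.4.21, 14.1.4.26 and 14.1.4.30. In the 18-49 stratum, under the age-only assumptions above, a simulation with a chi-square overall test gives a false 90 µg signal of only 2.8 to 2.9%. That also stands, so the age-only figures in step 6 describe the unstratified tables. What remains is period, the difference between 18-40 and 18-49, and the tables by SOC and PT, which have no age-group version. The 50-65 stratum has no 90 µg subjects by design, so a four-group test cannot be run there.

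**On the gate.** An overall test of all groups before pair-wise tests is conventional, and Section 2.14 records a deliberate choice. A reader might infer that the gate produces false differences among the retained groups. It does not in any phase-gap scenario in step 5: their false-pair rate never exceeds that of the three-group gate. Inflation needs a much larger 90 µg departure. With 50% in 90 µg against 30% elsewhere, a chi-square approximation gives 8.9% vs 5.5%. Nothing in the SAP suggests a gap of that size.

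**Conclusion.** The point holds and is minor.

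The wording conflict is certain, and it touches the critical value of the primary analysis. The power figures rest on Section 1.4's inputs and on equal 10% exclusion; without exclusion in placebo and 90 µg they change by no more than 0.1 point.

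Confounding of the 90 µg contrasts with phase, and partly with age, follows from the design. Its size is unknown, and every AE figure above rests on assumed rates. Under those rates a false 90 µg signal exceeds 5% only with the larger gaps, and the practical cost to the retained groups is about 4 to 6 points of power when there is no gap. A reader might also infer that the 135 µg, 180 µg and placebo estimates are biased. The documents do not support that: these groups were randomised together in both phases, with Run-in shares of 14% and 25%, so they are confounded with phase little or not at all. The AE tests are secondary, 90 µg was not carried into the Main Study, and no stated decision rests on its p-values.

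**What to change.** **Section 2.14:** replace the unrestricted sentence. State that inferential comparisons in immunogenicity (Section 5.3), and the pooled overall and pair-wise AE tests (Section 6.1.3), use 135 µg, 180 µg and placebo, with 90 µg shown descriptively.

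**Section 6.1.3:** change the four-group test to the same three groups.

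**If a 90 µg test is wanted:** restrict it to Run-in subjects, for example one Run-in-only version of Table 14.1.4.1 with 30 per group, and name it in Section 2.14 as the only comparison that includes 90 µg. Both sections have to change together; otherwise the mismatch moves to Sections 2.14 and 6.1.3.

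**Cost:** two short text edits. The 55 tested safety tables (14.1.4.1-43 and 14.1.4.48-59) keep their layout, and only the groups entering the test change. The downside is that 90 µg has no pooled p-value, and the Run-in-only comparison is less precise. At an assumed 35% rate, the 95% half-width for 90 vs 135 µg is 1.96 × √(0.35 × 0.65 × (1/30 + 1/30)) = 24 points, against 1.96 × √(0.35 × 0.65 × (1/30 + 1/210)) = 18 points pooled.

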2.15 Effect of COVID19 on the Interim Analysis

Possible impact of Covid-19 pandemic and respective measures were discussed and it was decided to not implement specific analysis measures for the interim analyses. Subject visits and time points analyzed in the IA D85 were completed before the pandemic started in the respective regions. IA D236 will be partly affected by the pandemic.

In particular, phone calls instead of on-site visits for time points after D85 were allowed and safety data for IA D236 are collected via phone call for a portion of the subjects. For IA Day 236, it will be tabulated and listed whether Visits were performed as a phone call (due to Covid-19) or on site.

The impact and analysis of availability of immunogenicity data and respective impact on trial results will be described in the SAP for Final Analysis.

[figure not shown]
In general, overviews on missing data, protocol deviations, missed visits, visits out of time-window and changes in study processes due to Covid-19 will be planned in the SAP for final analysis and described in the Final Clinical Study Report.

3. OVERALL STUDY INFORMATION

Analyses will be performed for the Safety Population, mITT Population and PP Population. If the Safety and mITT Populations are identical, the analysis will be performed for the Safety Population and the mITT Population together, labeled "Safety/mITT Population".

3.1 Data Points

The following information will be analyzed descriptively and corresponding details on the subject level will be provided in data listings:

- Subject overview (Analysis populations, countries)
- Screening failures and reasons
- Randomization
- Violated inclusion/exclusion criteria (will only be listed)
- Study vaccination details
- Visits log
- Attendance status and early termination details
- Protocol deviations
- Visits performed as phone call due to Covid-19 (only applicable for IA D236)

3.2 Definition

- Screening failures are defined as subjects not eligible for study enrolment.

4. BASELINE EVALUATION

Baseline data will be presented for the Safety, mITT and PP Population. If the Safety and mITT Population are identical (i.e. no mis-randomization) the analysis will be performed for the Safety Population and the mITT Population together, labeled with "Safety/mITT Population".

4.1 Data Points

The following information will be analyzed descriptively and corresponding details on the subject level will be provided in data listings:

- Demographic Information (gender, childbearing potential, age [years], race, body height [cm], body weight [kg] and body mass index [kg/m²])
- Physical examination (will only be listed)
- ECG
- Vaccination history
- Medical History
- Prior/Concomitant Medications
- Prior/Concomitant Procedures
- HIV (will only be listed)

4.2 Definitions

- Baseline for non-immunogenicity analyses is defined as Visit 0.
- Body height will be analyzed in centimeters (cm). Body height documented in inch (in) will be converted to cm using the following rule: height [cm] = height [in] × 2.54.
- Body weight will be analyzed in kg. Body weight documented in pounds (lbs) will be converted to kilogram [kg] using the following rule: weight [kg] = weight [lbs] × 0.45359237

- The Body Mass Index [kg/m²] will be calculated as (kg/cm²) × 10,000
- Medications stopped prior (<) to Day 1 (Visit 1) will be considered prior medications, all other medications are considered to be concomitant. Medications with a missing or incomplete end date where it cannot clearly be decided if the end date was before or after Day 1 (Visit 1) will be considered concomitant.
- Procedures stopped prior (<) to Day 1 (Visit 1) will be considered prior procedures, all other procedures are considered to be concomitant. Procedures with a missing or incomplete stop date where it cannot clearly be decided if the stop date was before or after Day 1 (Visit 1) will be considered concomitant.
- Medical history not stopped prior (<) to informed consent will be considered ongoing at study entry, Entries with a missing or incomplete stop date where it cannot clearly be decided if the stop date was before or after informed consent will be considered ongoing at study entry.

5. IMMUNOGENICITY ANALYSIS

All tables and figures will be provided for the PP Population. Specific tables and figures will be repeated for the mITT Population and will also be repeated stratified by baseline *B.b.* s.l. serostatus, region and by age group as marked in the list of TLFs in Section 7. Listings will include all subjects from the mITT Population. IA D85 will cover time points Day 1 (Visit 1) and Day 85 (Visit 4). No immunogenicity analysis will be performed for IA Day 236.

5.1 Data Points

5.1.1 Tables and Listings

[figure not shown]
The following ELISA information will be analyzed and corresponding details on subject level will be provided in data listings:

Summary tables for categorical immunogenicity variables:

- Immunogenicity blood sample availability by time point
- Immunogenicity results/serostatus (report concentration/negative) by OspA serotype by time point (including baseline serology status)
- Subjects by OspA IgG serostatus at baseline
- SCRs for OspA serotype specific IgG by visit
 - each OspA serotype (separate tables for ST1 to ST6)
 - all six OspA serotypes combined
 - ST1 and ST2 combined
- Subjects Reaching an at least 4-fold or a 10- Fold Increase from Day 1 (Visit 1) in OspA-specific IgG Titer by visit
 - each OspA serotype (separate tables for ST1 to ST6)

Summary tables for continuous immunogenicity variables will be provided:

- GMTs for IgG against each OspA serotype (ST1 to ST6) by visit (separate table for each OspA serotype).

- GMFRs as compared to Visit 1 (Day 1) for IgG against each OspA serotype by visit (separate tables for each OspA serotype)

Correlation Analysis:

- Correlation Analyses for each OspA Specific IgG titer with each other OspA Specific IgG titer, respectively, at Day 85 (15 comparisons in total)

Inferential analysis will be performed as described in Section 5.3. Details are specified in Section 7.

